### 7.2.1.4 Assessment of Intensity

Intensity refers to the degree of discomfort or impairment associated with an event. The intensity of MEs/AEs is to be reported on the CRF as mild, moderate, or severe, according to the definitions provided below. In addition, to maximize consistency in assessment, it is recommended that the National Cancer Institute (NCI) Common Terminology Criteria for Adverse Events (CTCAE) scale be used.

Intensity	Corresponding NCI CTCAE Grade
Mild: awareness of a sign or symptom but easily tolerated	1
Moderate: discomfort sufficient to cause interference with normal daily activities	2
Severe: resulting in inability to perform normal daily activities	3–5

### 7.2.1.5 Serious Adverse Events

An SAE is an adverse event occurring at any dose that results in any of the following outcomes:

- Death
- A life-threatening adverse event
- Inpatient hospitalization or prolongation of existing hospitalization
- A persistent or significant disability or incapacity
- A congenital anomaly in the offspring of a patient who received the study treatment
- An important medical event that does not result in death, is not life-threatening, and does not necessitate hospitalization but which in the investigator's judgment may jeopardize the patient and may necessitate medical or surgical intervention to prevent one of those outcomes. Examples include allergic bronchospasm requiring intensive treatment in an emergency room or at home, blood dyscrasias or convulsions that do not result in inpatient hospitalization, or the development of drug dependency or treatment-related substance abuse.

Clarifications:

- “Life-threatening” means that the patient was, in the view of the investigator, at immediate risk of death from the event as it occurred. This definition does not include an event that, had it occurred in a more severe form, might have caused death.
- Hospitalization for elective treatment of a pre-existing condition that did not worsen during the study is not considered an AE.
- Complications that occur during hospitalization are AEs. If a complication prolongs hospitalization, the event is considered an SAE.
- “Inpatient” hospitalization means the patient has been formally admitted to a hospital for medical reasons. This may or may not be overnight. It does not include presentation at a casualty or emergency room unless the event meets one of the other criteria for being an SAE.
- With regard to the criteria for an important medical event, medical and scientific judgment should be used in deciding whether prompt reporting is appropriate in this situation.

### 7.2.1.6 Reporting of Serious Adverse Events

All SAEs occurring up to 30 days following completion of or discontinuation from the study must be reported to the sponsor, regardless of whether they are suspected of having a causal

relationship with the study drug. Any SAEs for which the investigator does suspect a causal relationship must be reported to the sponsor regardless of the time elapsed since the last dose of the study drug.

Participants will be instructed to report SAEs to the investigator **within 24 hours**, by telephone. In turn, the investigator must report all SAEs to the sponsor **within 24 hours** of occurrence or notification by the participant, using the sponsor's SAE form. The sponsor will provide contact information for reporting SAEs. An assessment of causality must be provided at the time of the initial report. The investigator or delegate must then complete and submit a follow-up SAE form to the sponsor **within 5 calendar days**, and must submit further follow-up forms if additional relevant follow-up information becomes available.

The sponsor will submit reports of SAEs to the appropriate regulatory agencies, in line with local regulatory requirements and timelines.

Investigators must report all SAEs to their IRB/IEC as well as to the sponsor. If any SAE that is considered at least possibly related to the study medication and is unexpected occurs at one site, the sponsor will promptly inform all other sites of this, and all investigators must then report this event to their own IRBs/IECs, following the same timelines as above or following local IRB/IEC policy, whichever takes precedence.

#### **7.2.1.7 Follow-up and Documentation of SAEs**

SAEs that occur during the study and up to 30 days after the last dose of study drug must be documented in the patient's medical record and on the SAE report form. The investigator should attempt to establish a diagnosis of the event based on signs, symptoms, and/or other clinical information. In such cases, the diagnosis rather than the individual signs/symptoms should be documented as the SAE.

All SAEs must be followed until resolution, the condition stabilizes, the event is otherwise explained, or the patient is lost to follow-up. The investigator is responsible for ensuring that follow-up includes any supplemental investigations that may be indicated, in order to elucidate the nature and/or causality of the SAE as completely as possible. This may include additional laboratory tests or investigations, histopathological examinations, or consultation with other health care professionals. The sponsor may request that the investigator perform or arrange for the conduct of supplemental measurements and/or evaluations.

If a patient dies during participation in the study or during a specified follow-up period, the sponsor should be sent a copy of any post-mortem findings, including histopathology.

New or updated information is to be recorded on the originally completed SAE report form, with all changes signed and dated by the investigator.

The clinical research associate (CRA) will verify the original SAE report form against the source documents at the next monitoring visit.

## 7.2.1.8 Adverse Events of Special Interest

### 7.2.1.8.1 Neutropenia

Individuals taking deferiprone must be monitored for neutropenia, defined as a confirmed absolute neutrophil count (ANC) less than  $1.5 \times 10^9/L$ . Categories of neutropenia are as follows:

Mild neutropenia	A confirmed ANC < $1.5 \times 10^9/L$ but $\geq 1.0 \times 10^9/L$
Moderate neutropenia	A confirmed ANC < $1.0 \times 10^9/L$ but $\geq 0.5 \times 10^9/L$
Severe neutropenia / agranulocytosis	A confirmed ANC < $0.5 \times 10^9/L$

For a case of neutropenia to be confirmed, there must be 2 consecutive counts, a maximum of 3 days apart, that are both less than the specified value. If the 2 counts are not in the same severity category, a third count will be required to determine the severity. If a patient has just a single ANC value less than  $1.5 \times 10^9/L$ , this is to be documented in the CRF as an AE of “decreased ANC”, but is not to be defined as neutropenia. The investigator is to use judgment as to whether the decrease is clinically significant.

In addition to having ANC monitored, participants will be advised to immediately report any symptoms indicative of infection such as fever ( $\geq 38.0^{\circ}C$ ), sore throat, and flu-like symptoms at any time during the study and for one week following the last dose. They will be provided with an emergency services card with contact information, and advised to carry it with them at all times.

Depending on the severity of neutropenia, patients will either remain in or be withdrawn from the study. The management of different severities of neutropenia is described below.

**Mild neutropenia:** A patient who develops mild neutropenia is to interrupt treatment as soon as the neutropenia is confirmed, and ANC is to be monitored every 2 days until resolution.

The patient should re-initiate treatment once the event is resolved, defined as 2 consecutive  $ANC \geq 1.5 \times 10^9/L$ . If ANC is still  $< 1.5 \times 10^9/L$  after 14 days, the investigator is to do the following:

- Withdraw patient from the study and monitor him/her until resolution of the event
- Provide advice regarding protective isolation
- Examine patient the same day (if possible), including drug history and physical examination

- Notify ApoPharma Inc. using the SAE form

**Moderate neutropenia:** A patient in whom a single ANC measurement  $<1.0 \times 10^9/L$  but  $\geq 0.5 \times 10^9/L$  is detected is to immediately stop treatment, without waiting for confirmation of the count, and a second measurement is to be done within 48 hours. If the second ANC is still  $< 1.0 \times 10^9/L$ , the investigator is to do the following:

- Withdraw patient permanently from the study and monitor ANC daily until resolution
- Provide advice regarding protective isolation
- Examine patient the same day (if possible), including drug history and physical examination
- Notify ApoPharma Inc. using the SAE form

**Severe neutropenia/agranulocytosis:** A patient in whom a single ANC measurement  $< 0.5 \times 10^9/L$  is detected is to immediately stop treatment, without waiting for confirmation of the count, and a second measurement is to be done within 48 hours. If the second ANC is still  $< 0.5 \times 10^9/L$ , the patient is to be permanently withdrawn from the study, and ANC is to be monitored daily until resolution. The following procedures should be done by the investigator or the treating physician, as appropriate:

- Provide protective isolation; if clinically indicated, admit patient to hospital and obtain vital signs every 4 hours
- Examine the patient the same day, if possible, including drug history and physical examination
- With the consent of the parent/guardian (or patient, if applicable), collect a blood sample to attempt to identify genetic or other biomarkers related to agranulocytosis
- Notify ApoPharma Inc. using the SAE form.

The following additional measures describe a suggested medical management and monitoring:

- If possible, consider obtaining bone marrow aspirate for:
  - Histology
  - Progenitor culture
  - Frozen storage (1 mL sample)
- If possible, consider obtaining bone marrow biopsy (minimum length 3 mm)

- Perform septic work-up including chest X-ray, blood, urine, and throat cultures
- Obtain q4h temperatures from patient (monitored by family at home if patient is not in the hospital)
- If warranted, administer granulocyte stimulating factors, such as G-CSF 10 µg/kg, on an in-patient basis if possible, beginning the same day that the ANC is confirmed as  $< 0.5 \times 10^9/L$ ; administer daily until ANC is  $> 1.5 \times 10^9/L$  on 2 consecutive days
- If ANC  $< 0.5 \times 10^9/L$  for 7 days, repeat bone marrow biopsy and aspirate weekly during the period of agranulocytosis, if warranted

#### **7.2.1.8.2 Infections**

If a patient develops fever ( $\geq 38.0^{\circ}C$ ) or any sign of infection during the study, study product must be interrupted immediately, and neutrophil count should be obtained and monitored more frequently; every 2 days if ANC  $< 1.5 \times 10^9/L$ . Therapy can be re-initiated once all symptoms have been resolved, if the ANC is  $\geq 1.5 \times 10^9/L$ .

#### **7.2.2 Laboratory Measurements**

Analyses will be performed at a central laboratory, with the exception of the weekly or biweekly hematology assessments which may be performed at a local laboratory.

Investigators must interpret each report promptly (preferably within 24 hours) and must document their review by signing or initialing and dating it. Any laboratory values that fall outside a clinically accepted range, or that differ significantly from previous values, must be assessed for clinical significance, and must be marked by the investigator as either “CS” (clinically significant) or “NCS” (not clinically significant). Any clinically significant abnormalities or changes that are not part of a larger medical condition that is already recorded must be further explained on the laboratory report and documented as an adverse event in the eCRF.

Samples for laboratory safety assessments will be taken at the time points indicated below. If a patient withdraws from the study, the End of Study procedures are to be performed at an early termination visit.

Hematology: Hemoglobin, total WBC count, ANC, MCV, and platelet count	Screening and weekly after start of dosing up to Month 6 visit, then biweekly until Month 12 or early termination from the study
Blood chemistry: Total protein, GGT, glucose, bilirubin (total, direct, and indirect), AST, ALT, albumin, blood urea nitrogen, calcium, creatinine, total iron binding capacity, serum iron, zinc, and C-reactive protein (CRP)	Screening and Months 1, 3, 6, 9, and 12 (or end of study)
Urinalysis: pH, specific gravity, glucose, protein, ketones, blood, and (if indicated by the dipstick results), sediment microscopy. If there is blood in the urine or three or more “plus signs” for protein, samples must be sent for microscopy.	Screening and Month 12 (or end of study)
Serology: Hepatitis B, hepatitis C, HIV	Screening
Other: Prolactin	Baseline and Month 12

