### **Blood Draws for Hematology**

Hematology testing is to be done weekly (every  $7 \pm 3$  days) after start of dosing up to Month 6, and then biweekly (every  $14 \pm 3$  days) until termination from the study. On weeks that include a site visit, this testing will be done as part of the regular study procedures. On other applicable weeks, it may be done either at the site or at a local laboratory. The results are to be reviewed by the investigator as soon as they are received, preferably within 24 hours.

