### **5.3 Safety Endpoints**

The safety endpoints are:

- Adverse events (AEs): Frequency, intensity, time to onset, duration, and relatedness to study drug
- Serious adverse events (SAEs): Frequency, intensity, time to onset, duration, and relatedness to study drug
- Number of discontinuations due to AEs
- Growth parameters: Weight, height, and height velocity, as classified using the Z-score system
- Change in prolactin level from baseline to Month 12

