### 5.7.1 AEs and SAEs

Adverse events (AEs) are coded using MedDRA version 23.0 or higher. In counting the number of patients who experienced each AE, any patients who experienced the same AE multiple times will be counted only once for the corresponding preferred term (PT). Similarly, any patients who experienced multiple AEs within the same system organ class (SOC) will be counted only once for that SOC. AEs will be tabulated alphabetically by SOC; and within each SOC, the PTs will be presented alphabetically. In tables that present the incidence of AEs by severity, seriousness, and relation to study

medication, any patients with multiple events coded to a given PT or SOC will be counted only once for that PT or SOC according to the most severe event, the most serious event, or the event with the closest relationship to study medication.

AEs will be summarized for the total number of AEs, the total number and percent of patients who experienced at least one AE, and the total number and percent of patients who experienced an AE within each SOC (and each PT within an SOC). A p-value comparing the percentages of each AE among treatment groups will be calculated by using Fisher's exact test.

The incidences of AEs, SAEs, adverse drug reactions (ADRs), and serious ADRs (SADRs) will be tabulated by treatment group. The relationship to study medication for AEs will be tabulated by treatment group.

A listing of SAEs and a listing of withdrawals due to AEs with time to withdrawal will be produced. Any deaths will be listed separately and discussed in narratives.

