## **14.3 Safety analyses**

### **14.3.1 Adverse events**

Table 14.3.1.1 Overall summary of adverse events

Table 14.3.1.2 Adverse events

Table 14.3.1.3 Most common Adverse Events  $\geq 5$  percent

Table 14.3.1.4 Adverse events with the maximum severity/intensity

Table 14.3.1.5 Adverse drug reactions

Table 14.3.1.6 Most common Adverse drug reactions  $\geq 5$  percent

Table 14.3.1.7 Adverse drug reaction with the maximum severity/intensity

Table 14.3.1.8 Serious adverse events

Table 14.3.1.9 Serious adverse events with the maximum severity/intensity

Table 14.3.1.10 Serious adverse drug reactions

Table 14.3.1.11 Serious adverse drug reactions with the maximum severity/intensity

Table 14.3.1.12 Adverse events by relatedness to study medication

Table 14.3.1.13 Adverse events – event count and rate

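### Because ANC testing halves at Month 6 and deferiprone children should stay longer, the unsplit patient-year rate in SAP Table 14.3.1.13 can modestly understate deferiprone against placebo for short, symptom-free low-ANC events

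*Protocol*

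**What the plan says.** **Testing.** Protocol 7.2.2 sets haematology at "Screening and weekly after start of dosing up to Month 6 visit, then biweekly until Month 12 or early termination from the study". Protocol Table 5.1, the section on blood draws for haematology, and SAP 4.2.2 agree. The schedule is the same in both arms.

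**What becomes an event.** Under Protocol 7.2.1.8.1, for a single ANC below 1.5 x 10^9/L, "this is to be documented in the CRF as an AE of" decreased ANC; it is not called neutropenia. For confirmed neutropenia "there must be 2 consecutive counts, a maximum of 3 days apart", both low. On fever or any sign of infection, "neutrophil count should be obtained and monitored more frequently" (Protocol 7.2.1.8.2), whatever the month.

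**Who stays.** Children leave at serum ferritin of at least 1000 µg/L on two consecutive visits (Protocol 3.1 and 4.5). The sample size section (9.2) expects 70% of deferiprone and 20% of placebo children below that level at Month 12.

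**What is reported.** SAP 5.3 lists as an endpoint "Adverse events (AEs): Frequency, intensity, time to onset, duration, and relatedness to study drug". SAP 5.7.1 states: "A p-value comparing the percentages of each AE among treatment groups will be calculated by using Fisher's exact test". The table list adds "Table 14.3.1.13 Adverse events – event count and rate". Its shell has one rate per 100 patient-years per arm, with no split at Month 6, no count of tests and no p-value. The SAP gives no table or method for time to onset.

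**The concern.** A short, symptom-free dip in ANC is recorded only if a scheduled test falls inside it. Recorded events therefore depend on the number of tests as well as on risk. Dividing by patient-years corrects for unequal follow-up but not for unequal tests per patient-year. If deferiprone children contribute more of the two-weekly period, their rate is diluted more than placebo's.

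The stake is limited but real. Protocol 1.4 names agranulocytosis as the most serious event associated with the drug, and neutropenia is an adverse event of special interest. Table 14.3.1.13 is the adverse event display that adjusts for unequal exposure, so a reader will turn to it when the patient percentages are hard to interpret. Dose can also rise during follow-up (Protocol 3.1), so the period with fewer tests may include more time at the higher dose.

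**Working it through.** The plan states no figure for ANC detection. The retention figures come from the sample size statement, whose claim of over 90% power reproduces (99.1% by normal approximation, 98.3% by Fisher's exact test, 32 per arm).

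**Step 1, detection.** With tests every T days and an episode of fixed length D starting at random, the chance of detection is min(1, D/T). Let k be the detection chance at T = 14 divided by that at T = 7. Then k = 0.50 for D of 7 days or less, 10/14 = 0.71 for 10 days, and 1.00 for 14 days or more.

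**Step 2, exposure.** Months per child before and after Month 6, under three assumed exit patterns:
- A: constant exit to 70% and 20% retained at Month 12. With λ = −ln(0.7)/12 and −ln(0.2)/12, integrating exp(−λt) gives deferiprone 5.50 + 4.60 and placebo 4.12 + 1.84.
- B: same retention, with exits at Month 9 (deferiprone) and Month 7 (placebo). Deferiprone 6 + (0.7×6 + 0.3×3) = 6 + 5.1; placebo 6 + (0.2×6 + 0.8×1) = 6 + 2.0.
- C: the earlier study in Protocol 1.3, where controls reached 1000 at about 6 months and 10% of deferiprone children by 9 months. The two-visit rule adds a month: placebo 6 + 1.0; deferiprone 6 + (0.9×6 + 0.1×4) = 6 + 5.8.

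**Step 3, apparent rate ratio when the true ratio is 1.** With s the share of time after Month 6, ratio = [1 − s_D(1 − k)] / [1 − s_P(1 − k)].

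For A and short dips: s_D = 4.60/10.10 = 0.455 and s_P = 1.84/5.96 = 0.309, so (1 − 0.228)/(1 − 0.155) = 0.91.

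| Pattern | Two-weekly share, deferiprone v placebo | 7 days or less | 10 days | 14 days or more |
|---|---|---|---|---|
| A | 46% v 31% | 0.91 | 0.95 | 1.00 |
| B | 46% v 25% | 0.88 | 0.94 | 1.00 |
| C | 49% v 14% | 0.81 | 0.90 | 1.00 |
| Equal retention | equal | 1.00 | 1.00 | 1.00 |

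If episode lengths vary exponentially, the ratio in A is 0.95 for a mean of 7 days and 0.97 for 14; in C it is 0.89 and 0.93.

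**Step 4, the tested measure.** Assume 0.2 events per patient-year in both arms and use mean exposure. In A, with episodes of 14 days or more, the chance of at least one event is 1 − exp(−0.2×0.841) = 15.48% against 1 − exp(−0.2×0.497) = 9.46%, a ratio of 1.64. In B, with 7-day dips, effective years are (6 + 0.5×5.1)/12 = 0.7125 and (6 + 0.5×2.0)/12 = 0.583, giving 13.28% against 11.01%, a ratio of 1.21. Over A to C the range is 1.21 to 1.64, all above 1.

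**Step 5, precision.** Applying the pooled proportions in Protocol Table 1.1 to 32 children: neutropenia 32×54/860 = 2.0, neutrophil count decreased 32×55/860 = 2.0, agranulocytosis 32×18/860 = 0.7. A 95% Poisson interval around 2 events is about 0.24 to 7.2.

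**Step 6, effect of splitting.** Within a period both arms share one detection chance, so the apparent ratio returns to 1.00 in each period and in a period-stratified ratio. The late-to-early ratio within an arm is still k, so patient-year rates by period would show the testing change as a fall of up to half.

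**The case against.** The strongest reply is that the plan's between-arm test is Fisher's exact test on patient percentages, where longer follow-up pushes deferiprone up. This stands: the downward pull affects one descriptive table. It does not make that table right, since neither display alone gives a clean comparison.

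Second, fever or infection triggers an ANC at any time, and low counts are followed every 2 days. This stands for symptomatic episodes and for follow-up once a low count is found. It does not help find silent dips.

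Third, with about two expected cases, chance exceeds a 9 to 19% distortion. This also stands, and it limits the importance of the point.

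Fourth, the SAP already shows haematology by scheduled week (Table 14.3.6.1.1), the proportion abnormal at each assessment (Figure 14.3.1.2) and ANC graphs for affected patients. These help, but they are not adverse event rates by arm.

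Fifth, Protocol 7.2.1.8.1 leaves clinical significance to the investigator, and Protocol 7.2.1.1 and 7.2.2 make laboratory findings adverse events when judged significant. If sites apply that filter, fewer single low counts will be recorded.

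A reader might infer that the report will show neutropenia risk falling over time. The documents do not support this: Table 14.3.1.13 has one rate per arm, and no time-to-onset table is planned. A reader might also take controls to leave at Month 6 exactly, which gives 0.75, but exit needs two consecutive visits, so 0.81 is the defensible figure.

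**Conclusion.** The point holds in a narrow form. For symptom-free low-ANC events of 7 days or less, the pooled patient-year rate can show deferiprone against placebo at about 0.91 (planning rates, constant exit) to 0.81 (earlier-study pattern) when the true ratio is 1. The distortion shrinks as episodes lengthen and is absent when every episode lasts 14 days or more, or when retention is equal.

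These sizes assume a constant risk common to both arms, tests at exactly 7 and 14 days despite the ±3-day windows, and no symptom-triggered detection. Episode lengths and exit times are assumptions; the documents do not give them. It would go too far to say that the trial's safety comparison hides a deferiprone excess: the bias is confined to a descriptive table. Correcting it is worthwhile because its direction is known and the cost is small.

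**What to change.** In SAP 5.7.1 and Table 14.3.1.13, for ANC-defined events (decreased ANC, neutropenia, agranulocytosis):

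- Keep the full-period rate and add rates by arm for Day 0 to Month 6 and Month 6 to Month 12.
- For each period and arm, give patient-years, number of ANC tests and low results per test. Flag which low counts came from scheduled tests, because repeat tests after a low count would inflate the per-test figure.
- Compare arms within each period, or with a period-stratified rate ratio. Do not drop later events or restrict the comparison to the first six months.
- Add a note that patient-year rates are not comparable between periods because testing frequency changes. Without it, the split would itself suggest a falling risk.

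The cost is SAP wording and one more table with sparse counts. No new data are needed, and the monitoring schedule is unchanged.
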